9.2.4. Baseline Period

For each of the study cohorts, the baseline period will be defined as the 365 days prior to and including the cohort entry date. Recognizing that a narrower (for time-varying covariates, etc.) or broader (for chronic conditions, etc.) window of assessment may better capture select patient attributes of interest, select covariates may be assessed using alternate time period(s). Patients selected into more than one cohort (eg, RZV ≥ 1 Dose and RZV 2-Dose cohorts) will have separate baseline periods corresponding to each date of cohort entry.

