9.2.2. Exclusion Criteria

Patients meeting any of the following criteria will not be included in the study:

1. Receipt of RZV (comparator cohorts only in the RZV 2-Dose analysis) during the 365 days prior to cohort entry, excluding the cohort entry date;
2. Diagnosis of HZ infection in the 365 days prior to cohort entry, excluding the cohort entry date;
 - Presence of a diagnosis code for HZ infection on the same date as RZV receipt (Dose 1 or Dose 2) will not be cause for exclusion from the study due to the administrative claims process;
3. Receipt of a solid organ transplant or hematopoietic stem cell transplant during the 365 days prior to cohort entry, excluding the cohort entry date;

4. In addition, patients with any of the following claims-based indicators of disease flare during the 91 days prior to cohort entry (as described in Section 9.2.3.2.1 for the RZV 2-Dose analysis, and in Section 9.2.3.2.2 for RZV ≥ 1 Dose analysis) will not be included in the study:
- Emergency room visit or hospitalization with UC as primary diagnosis (UC cohorts);
 - UC-related surgery (ie, colectomy, proctocolectomy) (UC cohorts); and
 - Emergency room visit or hospitalization with RA as primary diagnosis (RA cohorts).

[figure not shown]
In addition, patients meeting any of the following criteria will not be included in the RZV 2- Dose analysis:

5. Diagnosis of HZ infection within 28 days after but not including the cohort entry date (ie, Days [1,28]), as the follow up time will be assessed from day 29 after cohort entry date (Section 9.2.5.1); and
6. Occurrence of any censoring event (ie, disenrollment from health plan, death, end of the study period, or receipt of RZV) within 28 days after cohort entry date (Section 9.2.5.1).

Figure 2 summarizes the schematic for assessing patient eligibility, as well as assessment of covariates and outcomes, for (a) the RZV 2-Dose analysis and (b) the RZV ≥ 1 Dose analysis, with details outlined in the subsequent sections.

Figure 2. Schematic for Assessing Eligibility, Covariates, and Outcomes of RZV Initiators and Comparators in (a) RZV 2-Dose Analysis and (b) RZV ≥ 1 Dose Analysis

(a)

- a. Up to 32 day gaps in medical or pharmacy enrollment allowed
- b. Receipt of RZV exclusion applied to Comparator cohorts only
- c. Baseline conditions included: healthcare utilization, comorbid conditions, and treatment history

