9.2.3.2. Exposure Cohorts

9.2.3.2.1. RZV 2-Dose Analysis

The RZV 2-dose analysis will be used to assess the primary objective for effectiveness.

Using UC patients as an example, patients who are current users of tofacitinib will be identified into the following 2 cohorts, based on receipt of RZV, as illustrated in [Figure 1](#):

1. UC RZV 2-Dose: UC patients who receive two doses of RZV; and

2. UC Comparator 2-Dose: UC patients who do not receive RZV and are time-matched (within a 4-week window) to patients in the UC RZV 2-Dose cohort.

Exposure cohorts among patients with RA will be identified using the same framework.

[figure not shown]
9.2.3.2.1.1. RZV 2-Dose Cohorts

Starting at the beginning of the study period (20 October 2017), Optum will identify the RZV 2-Dose cohorts by searching the pharmacy and medical claims records for RZV administrations among patients who are current users of tofacitinib (as defined in Section 9.2.3.1). Specifically, administrations of RZV that occur during tofacitinib on-treatment periods will be identified, as illustrated in Figure 3. A RZV administration will be defined as a second dose if a separate RZV administration is observed in the previous 1 to 6 months.⁹ Exposure to RZV will be identified as described in Section 9.3.4.

The RZV 2-Dose cohorts (UC or RA) will include patients who receive a second dose of RZV with the second dose occurring during a tofacitinib on-treatment period on or after the study initiation date. In the RZV 2-Dose cohorts, *the date of cohort entry will be set as the date of the second administration of RZV*. Additionally, to be eligible for the study, patients will have to fulfill additional criteria, as described in Sections 9.2.1 and 9.2.2.

While current tofacitinib exposure will be required at cohort entry (ie, receipt of second dose in the RZV 2-Dose cohort), the first dose of RZV will not be required to occur during a tofacitinib on-treatment period to be eligible for the RZV 2-Dose cohort. As shown in Figure 3, both example Patient 1 and Patient 2 are eligible for the RZV 2-Dose cohort at the time of receipt of the second RZV dose. Nonetheless, the main comparison will be the subgroup of patients whose treatment with tofacitinib overlaps with both doses of RZV relative to patients treated with tofacitinib who do not receive RZV (Section 9.7.3.1)

Figure 3. Examples of Patients Eligible for the RZV Cohort and/or Comparator Cohort

Tofacitinib exposed person-time

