9.2.3.2.2. RZV ≥ 1 Dose Analysis

The RZV ≥ 1 dose analysis will be used to assess the secondary objectives for effectiveness and safety.

Separate cohorts will be created to address the secondary objectives for effectiveness and safety comparing patients who receive at least one dose of RZV to patients who do not receive of RZV. Using patients with UC as an example and similarly to the RZV 2-Dose analysis, patients who are current users of tofacitinib will be identified into the following 2 cohorts, based on receipt of RZV, as illustrated in [Figure 1](#):

1. UC RZV ≥ 1 Dose: UC patients who receive at least one dose of RZV; and
2. UC Comparator ≥ 1 Dose: UC patients who do not receive RZV and are time-matched (within a 4-week window) to patients in the UC RZV ≥ 1 Dose cohort.

Exposure cohorts among patients with RA will be identified using the same framework.

9.2.3.2.2.1. RZV ≥ 1 Dose Cohorts

Starting at the beginning of the study period (20 October 2017), Optum will identify the RZV ≥ 1 Dose cohorts by searching the pharmacy and medical claims records for RZV administrations among patients who are current users of tofacitinib (as defined in Section 9.2.3.1). Specifically, administrations of RZV that occur during tofacitinib on-treatment periods will be identified, as illustrated in [Figure 3](#). Exposure to RZV will be identified as described in Section 9.3.4.

[figure not shown]
In the RZV ≥ 1 Dose cohorts (UC or RA), *the date of cohort entry will be set as the date of the first administration of RZV during a tofacitinib on-treatment period on or after the study initiation date, with no administration of RZV in the prior 365 days.* Additionally, to be eligible for the study, RZV initiators will have to fulfill additional criteria, as described in Section 9.2.1 and 9.2.2 and shown in [Figure 2\(b\)](#).

9.2.3.2.2.2. Comparator ≥ 1 Dose Cohorts

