9.3.4. Exposure to RZV

RZV will be identified using a comprehensive list of codes denoting RZV, including Current Procedural Terminology® (CPT)¹ codes on medical claims or NDCs on pharmacy claims. This approach was used in a previous claims-based study of RZV and is expected to be a valid measure of exposure since the cost of RZV is covered by commercial insurance.¹⁵

RZV will be assessed through the presence of the following procedure codes or NDCs in medical or pharmacy claims:

- CPT 90750 Zoster (shingles) vaccine, recombinant, sub-unit, adjuvanted, for intramuscular use;
- NDC 58160081912 SHINGRIX 50 MCG/0.5 KIT;
- NDC 58160082311 SHINGRIX 50 MCG/0.5 KIT;
- NDC 58160082801 SHINGRIX GE ANTIGEN COMPONENT 50 MCG VIAL;
- NDC 58160082803 SHINGRIX GE ANTIGEN COMPONENT 50 MCG VIAL;
- NDC 58160082901 SHINGRIX ADJUVANT COMPONENT VIAL;
- NDC 58160082903 SHINGRIX ADJUVANT COMPONENT VIAL.

¹ CPT copyright 2022 American Medical Association.

All rights reserved. Fee schedules, relative value units, conversion factors and/or related components are not assigned by the AMA, are not part of CPT, and the AMA is not recommending their use. The AMA does not directly or indirectly practice medicine or dispense medical services. The AMA assumes no liability for data contained or not contained herein.

CPT is a registered trademark of the American Medical Association.

RZV is a 2 dose vaccine; it is recommended that the second RZV dose be given 2 – 6 months after the first, or 1 – 2 months after the first if needed among people with weakened immune systems.⁹ Patients will be classified into exposure cohorts based on their exposure to the first or second dose of RZV. Since the procedure codes and NDCs used to identify RZV do not distinguish between doses, first and second doses will be identified based on the number of RZV administrations observed. The first dose will be defined as the first RZV administration during the study period with no RZV administrations in the prior 365 days, while second RZV doses will be those administrations that occur 1-6 months after the first dose. To account for delays in the vaccination schedule, a 30-day one-sided grace period will be applied such that RZV second doses will be identified up to 7 months after the first dose.

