9.3.6. Covariates

Members of the study cohorts will be described according to claims-based covariates. Unless otherwise specified, diagnoses will be identified through the presence of ICD-10 codes, while prescription medications will be identified through pharmacy dispensings or administrations. No over-the-counter medications will be assessed. Drug use and disease status will be

² CPT copyright 2022 American Medical Association. All rights reserved.

categorized as yes (code present) or no (no code present). Demographic attributes will be determined on the cohort entry date while other factors will be assessed during the 365-day baseline period, unless otherwise specified. In addition to the covariates listed below, the 50 most common diagnoses, procedures, and medications will be described during the baseline period.

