9.3.6.2. Healthcare Utilization

- Number of outpatient visits;
- Number of emergency department visits;
- Number of 3-digit diagnosis codes;
- Number of drugs dispensed;
- Hospitalizations;
 - Number of hospitalizations;
 - Number of inpatient days (among patients who have been hospitalized).

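### RZV claims fall inside the baseline window, so they enter vaccinees' utilization counts but never comparators', and the weighted comparison leans modestly towards the vaccine

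*Protocol*

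**What the plan says.** Section 9.2.4 of the protocol sets the covariate window: "the baseline period will be defined as the 365 days prior to and including the cohort entry date". Section 9.3.6 applies it to all non-demographic covariates unless another window is specified.

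The anchor date is a vaccination date for vaccinees. In the 2-dose analysis, "the date of cohort entry will be set as the date of the second administration of RZV" (Section 9.2.3.2.1.1). In the ≥1-dose analysis, "the date of cohort entry will be set as the date of the first administration of RZV during a tofacitinib on-treatment period" (Section 9.2.3.2.2.1). On spacing, Section 9.3.4 says that "second RZV doses will be those administrations that occur 1-6 months after the first dose", and with the grace period "RZV second doses will be identified up to 7 months after the first dose".

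Comparators are treated differently. The first exclusion in Section 9.2.2 reads "Receipt of RZV (comparator cohorts only in the RZV 2-Dose analysis) during the 365 days prior to cohort entry, excluding the cohort entry date". Section 9.2.3.2.1.2 gives comparators a random entry date in a 4-week window without RZV exposure, and requires no health-care contact on that date.

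Section 9.3.6.2 lists outpatient visits, 3-digit diagnosis codes and "Number of drugs dispensed" as counts, and Section 9.3.6 adds that "prescription medications will be identified through pharmacy dispensings or administrations". Section 9.7.1 names the covariates of Sections 9.3.6.1 to 9.3.6.4 as pre-specified for the propensity score. Section 9.7.2 gives each vaccinee a weight of 1 and each comparator e/(1−e). Nothing in the protocol takes RZV claims out of the counts.

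**The concern.** RZV is found from CPT codes on medical claims or NDCs on pharmacy claims (Section 9.3.4). Those same records feed the utilization counts, so part of the exposure is built into its own propensity covariates, and only in the vaccinated arm.

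Weighting then raises the comparators' real utilization to meet a vaccinee figure that is partly vaccine claims. Where utilization predicts the outcome, the weighted comparator rate is too high. HZ effectiveness is overstated, and in the ≥1-dose safety analysis a flare hazard ratio is pulled below its true value. Both errors favour RZV, in a study that is a post-marketing commitment to the FDA.

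The planned diagnostic does not help. The standardized difference, with its 0.1 limit, is computed on the recorded counts, and those are exactly what the weights equalize.

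**Working it through.** The plan gives no figure on this point, so there is none to reproduce.

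**Step 1: which RZV claims fall in the window.** Day 0 is an RZV date by definition. Dose 1 precedes dose 2 by at most 7 months, which is at most about 215 days and well under 365.

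| Analysis | RZV claims in vaccinee baseline | In comparator baseline |
|---|---|---|
| 2-dose (HZ) | 2 | 0 |
| ≥1-dose (HZ, flare) | 1 | 0 |

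**Step 2: which counts they reach.** A pharmacy NDC claim can add to drugs dispensed. Section 9.4.1 lists no diagnosis field for pharmacy claims, so it adds no visit or diagnosis. A CPT medical claim can add to outpatient visits and diagnosis codes, but adds no visit if the dose was given at an appointment that would have happened anyway. So a dose reaches a given count with some probability q below 1, which the documents do not give.

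**Step 3: what the weights do.** Let k be the number of doses in the window and σ the standard deviation of the true count. Suppose both arms have the same true distribution.
- Recorded vaccinee mean = true mean + kq.
- Weighting brings the comparators' mean, which contains no RZV claims, to that value.
- Hidden imbalance in true utilization ≈ kq/σ.
- With hazard multiplied by r per standard deviation, comparator rate inflation f ≈ r^(kq/σ).
- Apparent effectiveness = 1 − (1 − VE)/f, and a null flare ratio becomes 1/f.

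**Step 4: numbers.** Assumed, because the documents do not give them: mean 15 with σ = 10, or mean 20 with σ = 15; r = 1.2 to 1.4; q = 1 or 0.5. VE of 66.7% is taken from Section 9.5. Each range runs from σ = 15, r = 1.2 to σ = 10, r = 1.4.

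| Case | kq | Hidden imbalance kq/σ | f | VE 66.7% becomes |
|---|---|---|---|---|
| 2 doses, q = 1 | 2 | 0.13–0.20 | 1.2^0.133 = 1.025 to 1.4^0.20 = 1.070 | 67.5%–68.9% |
| 2 doses, q = 0.5 | 1 | 0.07–0.10 | 1.2^0.067 = 1.012 to 1.4^0.10 = 1.034 | 67.1%–67.8% |
| 1 dose, q = 1 | 1 | 0.07–0.10 | 1.012 to 1.034 | 67.1%–67.8% |
| 1 dose, q = 0.5 | 0.5 | 0.03–0.05 | 1.006 to 1.017 | 66.9%–67.3% |

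For example, 1 − 0.333/1.070 = 0.689. For flare (one dose in the window), a true ratio of 1 becomes 0.97 to 0.99 with q = 1 and 0.98 to 0.99 with q = 0.5.

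**Step 5: simulation check.** This used negative binomial counts, 200,000 vaccinees and 400,000 comparators with identical true distributions, a logistic propensity score with linear and quadratic terms, and weights e/(1−e). With two certain claims the recorded standardized difference was 0.01 or less, while the true one was 0.14 to 0.21. Inflation was 1.025 to 1.070. Two claims at q = 0.5 gave 1.012 to 1.034. With no added claims the bias was zero.

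**The case against.** **SAP detail.** What counts as a visit or a drug is programming detail. Section 9.2.4 allows other windows for selected covariates, and Section 9.7.1 leaves model details to the SAP. The SAP could indeed cure this. But the protocol itself fixes a window that includes day 0 as the default, and the permissive clause names neither a covariate nor a rule on vaccine claims.

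**Pruning.** Section 9.7.1 drops empirically found covariates that correlate with RZV receipt without being outcome risk factors. That covers vaccine and immunization codes as stand-alone covariates. It does not strip them from a total of visits, codes or drugs.

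**Size.** A reader might infer that every 2-dose vaccinee gains two units on all three counts and that the biases add up. The documents do not support that. A dose goes mainly through one channel, a dose at an existing visit adds no visit, and if codes or drugs are counted as distinct items two doses add at most one. Adding two for everyone is a ceiling on a single count. Other planned covariates (comorbidities, steroid dose, number of treatments) would also leave a visit count with a weaker residual association than assumed here. These points stand, and they are why the result is stated as modest.

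**Wording.** Nor do the weights select sicker comparators. They up-weight patients already sampled who use more care, and higher use means higher risk only if utilization predicts the outcome. Section 9.7.1 itself requires a retained covariate to be a known or suspected confounder.

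**Precision.** At 2,000 vaccinated person-years and VE of 66.7%, about 8 against 48 events are expected, with a log-Wald 95% interval of roughly 30% to 84%. The bias is small beside that. It is still systematic and does not shrink with more data.

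**Conclusion.** The point holds as a modest bias of known direction. Followed as written, the protocol puts RZV claims into vaccinees' utilization covariates and none into comparators', and the planned balance check cannot reveal it.

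The direction rests on the protocol's own weights and on utilization predicting the outcome. The size rests on assumed count distributions, a 1.2- to 1.4-fold hazard per standard deviation, and how often a dose reaches a given count. On that basis the 2-dose comparator rate is about 1% to 3% too high when each dose reaches the count half the time, and at most about 2.5% to 7% when both always do. VE of 66.7% then reads as about 67% to at most 69%. A steeper risk gradient would give more, but nothing in the documents establishes one. They do not support a claim that this would overturn the study's conclusion.

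**What to change.** In Sections 9.2.4 and 9.3.6.2, count the utilization covariates over days −365 to −1 in both arms. In both analyses, also remove the following from every utilization count, for dose 1 and dose 2 alike:
- RZV product and administration codes;
- the immunization-encounter diagnosis that goes with them;
- visits whose only service is RZV.

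Both parts are needed. Ending the window at day −1 alone leaves dose 1 inside the 2-dose baseline. Other covariates may keep day 0, since dropping it for diagnoses and treatments is a wider trade-off that this point does not require. A side benefit is that Section 9.2.5.2 starts flare follow-up on the entry date, so a day-0 hospitalization would no longer be both a utilization covariate and a possible outcome.

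The cost is a sentence in the text and a programming filter, with no new data. Genuine day-0 utilization is no longer counted, which is a small loss. The first day of the window should be aligned with the 365-day enrollment requirement, which includes the entry date.

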9.2.5. Follow-up

9.2.5.1. RZV 2-Dose Analysis

In the 2-dose analysis, the occurrence of the primary outcome, HZ, for each cohort member will be assessed from day 29 after cohort entry until the first occurrence of HZ, disenrollment from the health plan, death, end of the study period, or receipt of RZV (ie, receipt of a third dose for the RZV cohorts or a first dose for the UC comparator and RA comparator cohorts only). The start of follow-up for HZ will begin on day 29 to allow for development of an immune response following receipt of the second RZV dose.¹⁵

9.2.5.2. RZV ≥ 1 Dose Analysis

In the ≥ 1 dose analysis, the occurrence of the primary outcome, HZ, for each cohort member will be assessed from the day after cohort entry until the first occurrence of HZ, disenrollment from the health plan, death, end of the study period, or receipt of RZV (patients in the UC comparator and RA comparator cohorts only). As patients may receive a diagnosis code for HZ on the date of RZV receipt, HZ diagnoses on the cohort entry date will not be counted as outcomes.

The occurrence of the secondary outcome, disease flare, will be assessed from the cohort entry date until the first occurrence of disease flare, disenrollment from the health plan, death, end of the study period, receipt of RZV (patients in the UC comparator and RA comparator cohorts only), or 90 days after cohort entry.

Primary and secondary outcomes will be assessed independently of one another; occurrence of the primary or secondary outcome will not lead to censoring for the other outcome. Furthermore, HZ and disease flare outcomes will be assessed in the RZV 2-Dose and Comparator 2-Dose cohorts independently of the RZV ≥ 1 Dose and Comparator ≥ 1 Dose cohorts. Onset of HZ that occurs during person-time between the first and second RZV doses will be attributed to the RZV or Comparator ≥ 1 Dose cohorts, and not the RZV or Comparator 2-Dose cohorts (see Section 9.2.2). Tofacitinib discontinuation will not censor follow-up for either the primary or the secondary outcome.

9.3. Variables

9.3.1. Exposure to Tofacitinib

Tofacitinib treatment will be identified through the presence of National Drug Codes (NDCs) on pharmacy claims. In addition to dispensings of tofacitinib, other variables, such as duration of treatment and dose, will also be assessed as detailed in Section 9.2.3.1.

Tofacitinib will be assessed through the presence of the following NDCs in pharmacy claims:

- NDC 00069050114 XELJANZ XR 11 mg extended-release tablet;
- NDC 00069050130 XELJANZ XR 11 mg extended-release tablet;
- NDC 00069050230 XELJANZ XR 22 mg extended-release tablet;
- NDC 00069100101 XELJANZ 5 mg tablet;
- NDC 00069100201 XELJANZ 10 mg tablet;
- NDC 00069102901 XELJANZ 1 MG/ML oral solution;
- NDC 00069102902 XELJANZ 1 MG/ML oral solution.

9.3.2. Ulcerative Colitis

Patients will be eligible for the UC cohorts if, within the 365 days prior to and including their cohort entry date, they have at least one medical claim with a diagnosis of UC (ICD-10 code: K51*, Ulcerative colitis) in any position.

9.3.3. Rheumatoid Arthritis

Patients will be eligible for the RA cohorts if, within the 365 days prior to and including their cohort entry date, they have at least one medical claim with a diagnosis of RA (ICD-10 code: M05*, Rheumatoid arthritis with rheumatoid factor) in any position. In addition, M06* (other rheumatoid arthritis) will also be used, except M06.1 (adult-onset Still's disease) and M06.4 (inflammatory polyarthropathy).

9.3.4. Exposure to RZV

RZV will be identified using a comprehensive list of codes denoting RZV, including Current Procedural Terminology® (CPT)¹ codes on medical claims or NDCs on pharmacy claims. This approach was used in a previous claims-based study of RZV and is expected to be a valid measure of exposure since the cost of RZV is covered by commercial insurance.¹⁵

RZV will be assessed through the presence of the following procedure codes or NDCs in medical or pharmacy claims:

- CPT 90750 Zoster (shingles) vaccine, recombinant, sub-unit, adjuvanted, for intramuscular use;
- NDC 58160081912 SHINGRIX 50 MCG/0.5 KIT;
- NDC 58160082311 SHINGRIX 50 MCG/0.5 KIT;
- NDC 58160082801 SHINGRIX GE ANTIGEN COMPONENT 50 MCG VIAL;
- NDC 58160082803 SHINGRIX GE ANTIGEN COMPONENT 50 MCG VIAL;
- NDC 58160082901 SHINGRIX ADJUVANT COMPONENT VIAL;
- NDC 58160082903 SHINGRIX ADJUVANT COMPONENT VIAL.

¹ CPT copyright 2022 American Medical Association.

All rights reserved. Fee schedules, relative value units, conversion factors and/or related components are not assigned by the AMA, are not part of CPT, and the AMA is not recommending their use. The AMA does not directly or indirectly practice medicine or dispense medical services. The AMA assumes no liability for data contained or not contained herein.

CPT is a registered trademark of the American Medical Association.

RZV is a 2 dose vaccine; it is recommended that the second RZV dose be given 2 – 6 months after the first, or 1 – 2 months after the first if needed among people with weakened immune systems.⁹ Patients will be classified into exposure cohorts based on their exposure to the first or second dose of RZV. Since the procedure codes and NDCs used to identify RZV do not distinguish between doses, first and second doses will be identified based on the number of RZV administrations observed. The first dose will be defined as the first RZV administration during the study period with no RZV administrations in the prior 365 days, while second RZV doses will be those administrations that occur 1-6 months after the first dose. To account for delays in the vaccination schedule, a 30-day one-sided grace period will be applied such that RZV second doses will be identified up to 7 months after the first dose.

